3.5. Number of Subjects

Aim 1: We plan to enroll 15 patients in 3 months. In any given week, between 10 and 20 older patients with MN are receiving HMA at the Wilmot Cancer Institute. In a previous qualitative study conducted in this population, recruitment rate was close to 100%.⁸⁴ Therefore, we expect to be able to recruit 15 patients in 3 months.

Aim 2: Annually from 2012-2017, four oncologists saw approximately 150 patients with MN aged ≥ 60 at the Wilmot Cancer Institute, and 70% received outpatient HMA. In prior studies of older patients (including MN) enrolled on behavioral pilot intervention studies at our institution, the recruitment rate was 65-75%.^{85,86} Therefore, we expect to be able to recruit 25 patients in 18 months.

3.6. Gender of Subjects

The gender ratio of patients to be enrolled on the study will be similar to the gender ratio of myeloid neoplasms in older adults (approximately 1.2:1 Male to female ratio).⁸⁷

3.7. Age of Subjects

We will recruit patients with myeloid neoplasms aged 60 and above (from date of consent, confirmed on electronic medical record).

3.8. Racial and Ethnic Origin

Myeloid neoplams affects all races with similar rates. Whites, African American and Hispanics make up approximately 65%, 30% and 5%, respectively, of the older population in Rochester, New York.⁸⁸ As we limited enrollment to English-speaking patients, we anticipate a higher percentage of whites in our study. The study has no enrollment restrictions based upon race or ethnic origin.

3.9. Vulnerable Subjects

No special classes of subjects such as fetuses, neonates, children, pregnant women, prisoners, institutionalized individuals or other vulnerable populations will be recruited.

4.0. Recruitment and Consent

Subjects will be enrolled at the University of Rochester Medical Center (URMC) Wilmot Cancer Center and WCI-affiliated community practices such as Interlakes Oncology, Dansville, Pluta, Olean, Wellsville. Study subjects will be recruited from the malignant hematology clinics at WCI and general oncology clinics at WCI-affiliated community practices. We plan to enroll 40 subjects (15 in phase 1 and 25 in phase 2) over a course of 2 years.

To ensure appropriate safety precautions when conducting in-person study procedures, the process for conducting in-person visits outlined in the Guidance for Human Subject Research will be followed.

4.1. Identification of Study Subjects, Recruitment, and Consent Procedures

Study subjects will be identified in multiple ways. First, patients will be identified by their treating physician, the nurses that work with the physicians, and the study coordinator. The study coordinator will work closely with the physicians and nurses to identify those patients that are anticipated or have begun treatment with chemotherapy. Second, with permission from oncology providers, we will screen for eligible patients from clinic schedules. The study coordinator contacts the physician (or their designee) and informs them that a patient may be eligible for the study. The physician (or their designee) then confirms if the patient is a study candidate or not (including whether they are a candidate to exercise). This will be documented in the subject research chart. If there is a question about eligibility, the principal investigator will be contacted and will meet with the patient, review the medical records, and perform an assessment of eligibility if necessary. The same identification process will be used for all sites.

For in-person consent, below are the possible scenarios for obtaining consent.

- 1) Physician/Study Investigator makes the initial contact andprovides consent form, and patient signs consent with the physician on the same day: After confirming with the physician (or their designee) that a patient is a potential candidate for the study, the study staff will provide a consent form to the treating physician/study investigator so he/she can provide it to the patient during an in-person clinic visit. The physician/study investigator will go over every detail of the study during the clinic visit with patient. If agrees, the patient will sign the consent form with the physician/study investigator during the same in-person visit.
- 2) Study staff makes the initial contact and provides consent form, and patient signs consent with the study staff on the same day:

After confirming with the physician (or their designee) that a patient is a potential candidate for the study, the patient will be provided with an informed consent form by the study staff when they come in for an in-person clinic visit. The study staff will introduce the study to the patients and go over every detail of the study. If agrees, the patient will sign the consent form with the study staff during the same in- person visit with the study staff.

For **verbal consent**, below are the possible scenarios for obtaining consent. Generally two in-person visits are required prior to the start of intervention (the first in-person visit is to provide the wearable tracker and actigraphy, the second inperson visit to perform the in-person assessments and provide the tablet). By allowing verbal consent, we will be able to mail the wearable tracker and actigraphy to the patient.

- Physician/Study Investigator makes the initial contact, study staff follows up with the patient on the phone, and patient provides verbal consent on the phone: After confirming with the physician (or their designee) that a patient is a potential candidate for the study, the physician/study investigator confirms with the patient that he/she is willing to speak with the study staff about the study. The study staff will then call the patient via phone. The study coordinator will use the verbal consent script as a written aid and will go over every detail of the study with the patient to recruit them for the study. Study staff will sign and date it to confirm that he/she followed the script and the patient agrees to participate in the study. An information sheet summarizing the study and patient's involvement will be mailed /emailed to the patient for their records.
- 2) Physician/Study Investigator makes the initial contact and provides consent form, study staff follows up with the patient on the phone, and patient provides verbal consent on the phone: After confirming with the physician (or their designee) that a patient is a potential candidate for the study, the study staff will provide a consent form to the treating physician/study investigator so he/she can provide it to the patient during an in-person clinic visit. If the patient is interested but does not want to consent on the same day, the patient will bring the consent form home. The study staff will then call the patient via phone. The study coordinator will use the verbal consent script as a written aid and will go over every detail of the study with the patient to recruit them for the study. Study staff will sign and date it to confirm that he/she followed the script and the patient agrees to participate in the study. An information sheet summarizing the study and patient's involvement will be mailed/emailed to the patient for their records.

3) Study staff makes the initial contact and provides consent form, study staff follows up with the patient on the phone, and patient provides verbal consent on the phone: After confirming with the physician (or their designee) that a patient is willing to speak with the study coordinator about the study, the patient will be provided with an informed consent form by the study staff when they come in for an in-person clinic visit. If the patient is interested but does not want to consent on the same day, the patient will bring the consent form home. The study staff will then call the patient via phone. The study coordinator will use the verbal consent script as a written aid and will go over every detail of the study with the patient to recruit them for the study. Study staff will sign and date it to confirm that he/she followed the script and the patient agrees to participate in the study. An information sheet summarizing the study and patient's involvement will be mailed/emailed to the patient for their records.

4.1.1. Informed Consent

Informed consent will be obtained from the patient by the study investigators or coordinators. Consent documents will be signed by the patient and maintained in the patient record with copies provided to the patient. For verbal consent, documents will be maintained in the patient record with copies provided to the patient.

4.1.2. Baseline Measures and Study Procedures

After consent, the patient will complete baseline measures. Study coordinator will be available to assist the patient. The study coordinator will obtain information necessary to complete the forms capturing clinical data from the patient's medical records when the patient is unable to provide this information in sufficient detail (e.g. type of myeloid neoplasms, antecedent hematologic malignancies, treatment regimen).

For patients consented at Olean, Wellsville, and Dansville, they will be asked to meet with the study coordinator at the Wilmot Cancer Institute/Strong Memorial Hospital to conduct research activities. No research activities will be conducted at these sites.

4.1.3. Human Subject Protection

Ethical standards for human subjects will be strictly followed in accordance with the University of Rochester Research Subject Review Board Investigator Guidance policy.⁸⁹

4.1.4. Participation

Current state, federal, and institutional regulations concerning informed consent will be followed. Participation in this study is voluntary. Participants are free not to take part or to withdraw at any time, for whatever reason, without risking loss of present or future care they would otherwise expect to receive. In the event that a patient does withdraw from the study, the information they have already provided will be kept in a confidential manner. Participants may discontinue participation in the study at any time if they decide they do not wish to take part any longer. Participants may be withdrawn from the study by research personnel if it is deemed in their best interest to no longer participate.

4.1.5. Duration

Aim 1: The qualitative portion of the study will involve one semi-structured interview. Interviews with the patients will be held in person in a private space (clinic or office space). Interviews will be audio-recorded and led by study investigators and will last 30 minutes. These recordings will be uploaded to Box, and the recordings will be deleted from the audio-recorder.

Aim 2: Study participants will be consented to actively participate, receive phone calls or meet with the research study team at the baseline visit (week 0) and 8 ± 4 weeks after the intervention (week 8 ± 4). The research team may contact participants in the future to gain further information first hand regarding patients' overall health and treatment, the study team may decide to take participants off the study without their consent if the study is stopped. Additionally, study participant data will be kept for 7 years at URMC, even after the study is closed or a study participant passes away. It will be maintained in a locked database with password access only (See Section 9).

5.0. Registration

5.1. To register a participant who meets the eligibility criteria and who has signed the informed consent document, study staff will log on to OnCore and enter the information outlined in section 5.2 below.

5.2. Information Requested at Registration

- 5.2.1 Site
- 5.2.2 Most recent IRB approval date
- 5.2.3 Eligibility verification
- 5.2.4 Verification that consent form has been signed and who signed by (patient and/or health care proxy) and date signed
- 5.2.5 Treatment facility (Wilmot Cancer Center)
- 5.2.6 Participant's identification
 - 5.2.6.a First and last names
 - 5.2.6.b Birth date (MM/DD/STREAM)
 - 5.2.6.c Gender
 - 5.2.6.d Race
 - 5.2.6.e Five-digit zip code
 - 5.2.6.f Medical Record Number
 - 5.2.6.g Ethnicity
 - 5.2.6.h Patient's preferred and alternate phone numbers
 - 5.2.6.i Date of baseline Visit

5.3. Initial Assessment

After consent procedures are completed, the patient, with the help of the study coordinator, will complete a baseline assessment (see Section 7.2). Patients who are eligible will be enrolled and complete study procedures. For Aim 1, this will involve one semi-structured interview. For Aim 2, patients will be provided with the intervention and will be asked to complete post-intervention assessment at week 8 (\pm 4 weeks).

6.0. Intervention

6.1. EXCAP Exercise Program

The first component of the EXCAP exercise program is an individually tailored walking prescription and provides low to moderately intense aerobic exercise (3-5 exercise rating of perceived exertion on the American College of Sports Medicine [ACSM] revised rating scale, which is a visual analog scale ranging from 1 = "Not tired at all" to 10 = "So tired, I can't go anymore") 7 days a week. This walking prescription will be developed and individually tailored for each subject according to step data reported on the web portal. A Garmin activity tracker, a wearable sensor-based device, will be used record the number of steps they walk daily during the 4-7 days baseline assessment and then with the help of an exercise physiologist to calculate the average number of steps they walk daily during that period. The wearable devices will be registered by the research team (no phone or mobile identification numbers will be stored with data, and no GPS data will be collected to identify locations). Using the baseline average number of steps walked daily, patients are encouraged to increase their total steps walked by a minimum of 5% per week, while maintaining a moderate intensity. Subjects are encouraged to reach the ACSM suggested 10,000 steps a day if possible (this is not mandatory). As an instructional and motivational tool, at the start of the exercise intervention, a table will be provided that includes the average number of steps walked at baseline, as well as, the number of steps that would represent increases of 5%, 10%, 15%, and 20% over this baseline amount for each of the 8 weeks of the intervention period

The second component of the exercise program is an individually tailored therapeutic resistance band exercise prescription designed to provide low to moderately intense progressive resistance exercise [3-5 exercise rating of perceived exertion (RPE) on the ACSM revised rating scale] 7 days a week. Subjects are given a set of 3 color-coded therapeutic resistance bands representing varying levels of resistance. The exercise physiologist will explain the proper use of the resistance bands, safety, and the appropriate mechanics for performing the resistance training exercises. Subjects are instructed to begin with an individually determined number of sets (1 set = 8-15repetitions) for each of the sixteen exercises at a moderately challenging level (RPE=3-5) 7 days a week. The exercises target the upper and lower body. The exercise physiologist will work with the subject to find an optimally challenging number of sets and repetitions with the appropriately colored resistance band for each exercise with each patient. Subjects are instructed to increase the intensity by changing to a different color band or by shortening the initial length of the band for increased resistance. They are encouraged to progressively increase from their individual baseline sets and repetitions to a maximum of 4 sets of 15 repetitions for each exercise daily over the course of the 8-week (± 4 weeks) intervention at a rate that is optimally challenging. The therapeutic resistance band exercise prescription will be developed and individually tailored for each subject by the exercise physiologist. Each subject will report the intensity of their resistance exercise using 1) the rated perceive exertion (RPE) scale and 2) time spent for resistance band exercise by entering these data directly on the tablet.

6.2. PointClick Care Mobile App

PointClick Care is a mobile app that is preloaded on a tablet. The app was initially designed with the goal of helping people live independently. The app provides assistance in managing medications, chronic health conditions, doctor appointments, and activities of daily living including reminders to exercise. The PointClick Care app is connected to a data plan (which will be paid for by the study) for internet access, as well as a web portal that is accessible using a desktop or laptop computer of which internet access is required. The University of Rochester IT department has been contacted. As per the University policy for devices, the hard drive must be encrypted to protect any patient data. PointClick Care encrypts all PointClick Care data transferred between backend servers and the tablets. Communications to the server is validated by signed trusted server certificate. Data at rest is always encrypted. PointClick Care caches data on the tablet, and stores data on a PointClick Care server. On the tablet the cache in encrypted, the backend server hosts a Microsoft SQL Server database. The volume used by SQL Server is encrypted. Only the PointClick Care app, with a valid authentication key, can read this data. PointClick Care has a means to disable the PointClick Care app on a tablet. This feature only works, however, if the Tablet is connected to the server.

6.2.1 Tablet Device

The tablet device contains the PointClick Care app. The default screen displays the schedule for the day including doctor appointments, to-do-list and reminders (such as taking medications, or exercising) (Figure 2). Activities displayed on the tablet can only be entered through the web portal (i.e. have you walked at least 4000 steps today?). Users can select whether the tasks are completed on the tablet and they can manually enter the number of daily steps. The system also allows the user to create questionnaires.

Figure 2: Default screen of the **PointClick Care** application

"To do" includes: Medication, Weight, Blood Sugar and Blood Pressure activities.
 "Appointment" includes: Social Events and Doctor appointments.

6.2.2. Web-Portal

The web portal is accessed through a web address (https://client.PointClick Caresolutions.com) using a computer by the investigators and exercise physiologist and/or patients if they wish. The homepage displays the patient's information and a list of activities followed by the date and time, and whether the tasks have been completed (Figures 3 and 4). This function will allow the exercise physiologist to monitor for exercise adherence at a distance.

Figure 3: Homepage of the web-portal

User can access the profile by clicking "see more..." or "details". There are several functions on the web portal (Figure 3). The toolbar includes "home", "calendar", "medications", "health", "contacts", "alerts" and "reports". Under "calendar" tab, activities can be entered as events (e.g. have you walked at least 4000 steps today). Events can be entered as single or recurring events, and this can be displayed as a day or month view. Under "medications" tab, a list of the medications can be entered along with the time, strength, dosage, frequency and indication. Users are reminded to take their medications from the tablet device, and enter their compliance to generate a compliance report. Under "health" tab, vital signs or point of care information such as weight, blood pressure or blood glucose levels can be entered through the tablet, or electronically linked from the a monitoring system (weighing scale, glucometer or blood pressure cuff) to the web portal. A questionnaire can also be generated and questions can be tailored to cancer patients i.e. pain level measured using a Likert-scale. Under "contacts" tab, user can enter caregivers or healthcare teams' contact information, and they can be contacted directly from the tablet. Finally the "report" tab generates reports on all the aforementioned functions. Of note, automatic reminders can be generated and sent to providers if tasks are not completed or certain threshold of vital signs are met. For the purpose of this study, we are asking patients to enter their exercise data. They are encouraged to use other functions to assist with care coordination but are not required to do so.

Figure 4: Main profile page on the PointClick Care web portal

	EVENII	HISTORY				
:00 PM EDT	08/10	Evening Medications	•	08/10 8:30 PM	Not Done	
DO PM EDI	08/10	Check your port for infection	1.0	08/10 4:30 PM	Not Done	
2	08/10	Afternoon Medications	b.	08/10 2:30 PM	Not Done	
9	08/10	Morning Medications	••	08/10 10:00 AM	Not Done	
2 12	08/10	CT scan		08/10 12:02 AM	Done	
S.12	08/09	Check your port for infection		08/09 8:51 PM	Done	
	08/09	Morning Medications	••	08/09 8:51 PM	Done	
	08/07	Morning Medications		08/09 8:50 PM	Not Done	
	08/06	Evening Medications	••	08/06 8:30 PM	Not Done	
	08/06	Drink a glass of water	9	08/06 2:55 PM	Done	
	08/06	Check your port for infection	- Ce	08/06 2:43 PM	Done	
	08/06	Afternoon Medications		08/06 2:39 PM	Done	

6.3. GO-EXCAP Mobile App

We plan to integrate the content of the EXCAP exercise program into the PointClick Care mobile app (Figure 5). Older patients will participate in the EXCAP exercise program and enter exercise data into the mobile app. In addition, they will complete a symptom inventory and enter any barriers to exercise into the mobile app weekly. The study team (physiologist) logs into the web portal 2x/week to monitor intervention adherence, provide feedback, and adjust exercise prescriptions. These recommendations are available to the patients - they are automatically displayed via the mobile app daily. Patients can interact with the physiologist directly or via the mobile app.

Symptom reporting and management is an important component of our intervention because symptoms are common barriers to exercise. Based on our pilot data,^{16,90} we selected 15 common symptoms experienced by patients with MN based on the Patient-Reported Outcomes version of the Common Terminology Criteria for Adverse Events (PRO-CTCAE).⁹¹ We will assess symptoms weekly. These symptoms will be recorded on the web portal (described above). Study coordinator will log on to the web portal at least weekly to ensure that the symptom surveys are being completed. If the symptom surveys are not completed, the study coordinator will remind the patient during the weekly calls. For each symptom, we will use standardized severity-based algorithms and self-management strategies based on established protocols (Figure 6).^{92–94} A symptom report will be generated at clinic visits. In addition, these reports will be provided to the clinic nurses on a weekly basis.

Therefore, the mobile app serves as a tracking, teaching, and self-management device that is tailored to the individual. We will adapt the intervention content, format, and delivery of the app based on feedback from patients.

In the case that participants are unable to use the PointClickCare mobile app (i.e. company no longer operating), we will administer the exercise surveys and symptom inventories as REDCap surveys. The surveys will be disseminated via email. If the PointClickCare mobile app is no longer available, current subjects who are enrolled in the study will transition to use of the REDCap surveys and will terminate use of the mobile app. The previously collected data and subsequent analysis will remain unaffected and there will be no changes made to the study aims. Current subjects will be verbally notified of this change.

[figure not shown]

Figure 5: Proposed GO-EXCAP Mobile App

Figure 6: Example of severity-based algorithm/self-management strategies

In the last 7 days, what was the SEVERITY of your FATIGUE, TIREDNESS, OR LACK OF ENERGY at its WORST?

None	Mild Moderate	Severe Very Severe
No advice	 Did the fatigue stop you from exercising? Have you had recent blood work? Assess pain, distress, sleep hygiene, and nutrition Review energy conservation, sleep hygiene, physical activity, nutrition, etc. 	 Did the fatigue stop you from exercising? Same as mild/moderate If you have not already contacted your medical team, we recommend you to contact them

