2.2. Secondary Aim

To assess the feasibility of a mobile health exercise intervention (GO-EXCAP Mobile App) over 8 ± 4 weeks in a single-arm pilot study in 25 patients with myeloid neoplasms receiving outpatient chemotherapy (including HMA).

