2.2.1. Hypothesis

The GO-EXCAP Mobile App will be feasible in older patients with myeloid neoplasms receiving outpatient chemotherapy.

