2.2.1. Feasibility metrics

The feasibility of the GO-EXCAP Mobile App will be evaluated based on the following:

a) Percentage of patients wearing the activity tracker and entering resistance exercise data into the mobile app.

b) Percentage of patients performing both walking and resistance exercises during the study period days.

c) Recruitment rates (percentage of patients who are approached and agree to enroll).

d) Retention rates (percentage of patients who are enrolled and complete postintervention assessments).

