The feasibility of the GO-EXCAP Mobile App will be evaluated based on the following: a) Percentage of patients wearing the activity tracker and entering resistance exercise data into the mobile app and b) Percentage of patients performing both walking and resistance exercises during the study period days. Recruitment rates (percentage of patients who are approached and agree to enroll) and retention rates (percentage of patients who are enrolled and complete post-intervention assessments) will also be described

We will consider the intervention feasible if 1) \geq 70% of patients wear the activity tracker and enter resistance exercise data into the mobile app on at least 50% of the study period days, and 2) \geq 70% of patients performed both walking and resistance exercises on at least 50% of the study period days. We chose these criteria based on our previous mobile app study¹⁶ and on published exercise studies in older patients with AML.^{29,30} We will report percentage of adherence with 95% exact confidence interval (CI) calculated by the Clopper-Pearson method. We anticipate that about 20-30% of the participants will withdraw before post-intervention assessment due to rapid disease progression or death. These patients will not be included in the feasibility analysis because their withdrawals from the study are not related to the intervention. With 25 patients enrolled we anticipate at least 17 patients to be evaluable for our feasibility aims. When we estimate the percentage of adherence, a 95% CI will span approximately +/- 25%. For example, if we observe 12/17 (71%) patients complete the tasks, the CI will be 44-90%.

We will also tabulate the recruitment rates, retention rates, and intervention usability, and collect the reasons patient decline to be enrolled. In addition, we will evaluate the distribution and describe the following measures using descriptive statistics: 1) activity levels, 2) physical function (SPPB/vSPPB), 3) fatigue (BFI), 4) depression (CES-D Scale), 5) quality of life (FACT-Leu), and 6) Other geriatric assessment measures. Differences in activity levels, physical function, fatigue, depression, quality of life, and other geriatric assessment measures between pre- and post-treatment will be assessed using paired t-tests or Wilcoxon signed rank tests. Anticipated sample size of more than 12 patients with baseline and follow-up data will be sufficient to obtain the preliminary estimates of the outcomes measures.^{115,116}

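### Does a switch from the app to emailed REDCap surveys undermine feasibility criterion 1, which is worded as entry into the mobile app?

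*Combined protocol and SAP*

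**What the plan says.** Section 6.3 sets out what happens if patients cannot use the app, for example because the company has closed: "we will administer the exercise surveys and symptom inventories as REDCap surveys". The surveys go out by email. Patients already enrolled "will transition to use of the REDCap surveys and will terminate use of the mobile app". The paragraph closes with the assurance "The previously collected data and subsequent analysis will remain unaffected and there will be no changes made to the study aims".

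Section 8.2.2 gives two conditions for calling the intervention feasible. The first is that at least 70% "of patients wear the activity tracker and enter resistance exercise data into the mobile app on at least 50% of the study period days". The second, also set at 70% of patients and 50% of days, concerns walking and resistance exercise performed and does not mention the app. Metric (a) in the feasibility metrics of section 2.2.1 has the same app wording as criterion 1: "Percentage of patients wearing the activity tracker and entering resistance exercise data into the mobile app". The secondary aim (section 2.2) is "To assess the feasibility of a mobile health exercise intervention (GO-EXCAP Mobile App"), and the hypothesis in section 2.2.1 is "The GO-EXCAP Mobile App will be feasible in older patients with myeloid neoplasms receiving outpatient chemotherapy".

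Section 8.2.2 does not mention REDCap entries, switched patients, or whether the count of days stops at a switch.

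**The concern.** Taken word for word, 6.3 and 8.2.2 do not fit together. After a switch nobody enters anything in the app, so no later day can count toward criterion 1. A patient who exercises and reports faithfully, but is moved to REDCap before half of the study days have passed, would be scored as non-adherent for a reason unrelated to the patient or to the intervention. If REDCap entries are counted instead, criterion 1 no longer measures entry in the app alone, although the aim and hypothesis name the app. On either count, the statement that the analysis is unaffected seems too strong for this criterion.

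Criterion 1 is one of the two conditions behind the feasibility verdict, and about 17 evaluable patients are expected. At that size a single patient can decide a 70% threshold. A counting rule left open until the data are known could be chosen to suit the result.

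**Working it through.** **Reproducing the plan's figure.** Inputs from section 8.2.2: 25 enrolled, 20-30% withdrawal, Clopper-Pearson 95% intervals, 70% threshold. At 30% withdrawal, 25 × 0.70 = 17.5, which agrees with at least 17 evaluable. The plan's example is "if we observe 12/17 (71%) patients complete the tasks, the CI will be 44-90" percent. With lower limit the 2.5% quantile of Beta(x, n − x + 1) and upper limit the 97.5% quantile of Beta(x + 1, n − x), x = 12 and n = 17 give 70.6% (44.0-89.7%). The figure is reproduced.

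**When the literal wording bites.** If a patient is switched after day d of an L-week course, the largest possible share of days with app entry is d/(7L). I assume that study period days are all calendar days of the intervention, which section 8.2.2 does not spell out. Setting the share to 50%:

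| Course | Days | 50% reached at |
|---|---|---|
| 4 weeks | 28 | day 14 |
| 8 weeks | 56 | day 28 |
| 12 weeks | 84 | day 42 |

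A patient switched earlier cannot pass on app entries alone. A patient who already has app entries on half of the days is not harmed.

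**Effect on the verdict.** The minimum pass is 0.70 × 17 = 11.9, so 12 of 17. Suppose that one of the passing patients was switched early:

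| Count used | Result | 95% CI | At least 70%? |
|---|---|---|---|
| REDCap entries counted | 12/17 = 70.6% | 44.0-89.7% | yes |
| App entries only | 11/17 = 64.7% | 38.3-85.8% | no |
| Patient set aside | 11/16 = 68.8% | 41.3-89.0% | no |

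12/17 is the smallest passing count, so losing any one patient for any reason reverses it. From 13/17 (76.5%), losing one leaves 12/17, still a pass. It takes six early switchers to make a pass impossible at n = 17, since (17 − 6)/17 = 11/17 = 64.7%.

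**Which reading section 6.3 supports.** It names the exercise surveys as what moves to REDCap, keeps the aims unchanged and says that analysis goes on. That fits REDCap as a substitute route for the same data. The reading under which vendor closure turns adherent patients into failures is the one this paragraph supports least. A further possibility is that the sentence refers to analysis of the data collected before the switch, in which case it is simply true.

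**Would a stricter rule help?** One alternative is to judge switched patients on app days only, subject to a minimum number of such days, and to set the others aside. Its rationale would be that few app days make the pass mark unreliable. Assume independent days and a patient who logs on 60% of them, with a pass at 50% or more of app days. The probability of passing is then:

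| App days | 2 | 3 | 4 | 5 | 6 | 7 | 8 | 14 | 28 | 56 |
|---|---|---|---|---|---|---|---|---|---|---|
| P(pass) | 84% | 65% | 82% | 68% | 82% | 71% | 83% | 85% | 90% | 95% |

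The low values fall on odd day counts, where at least half means 2 of 3, 3 of 5 or 4 of 7. Two app days do about as well as fourteen, so over the first two weeks the series points to no natural minimum. Setting the patient aside also gives 11/16 = 68.8%, so vendor closure would still turn the plan's example into a fail.

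**The case for a change.** The strongest argument for a change is that the sponsor thought app closure likely enough to write a contingency, that the two sections conflict as worded, and that one sentence in 8.2.2 would settle the count before any data are seen. The only exclusion that 8.2.2 describes is withdrawal through rapid progression or death, so a switched patient who stays in the study remains in the denominator. REDCap is also not a full replacement: section 6.3 describes the app as showing recommendations daily and supporting teaching and self-management, and it does not say how often the emailed surveys are sent, although criterion 1 is counted in days.

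The textual point stands: the counting rule is unstated. The rest carries less weight. The 8.2.2 verdict is on the intervention, which is itself revised after every five patients, so the app is not a fixed object that a change of entry route would spoil. The tracker-wear half of criterion 1 does not depend on app entry. Under section 7.1 the physiologist's recommendations can also be given directly and the coordinator calls weekly, so any loss of support is partial. Extending the worry to criterion 2 and the pre/post measures is speculation, since neither is defined by app entry.

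**Conclusion.** The concern does not call for a change. The plan leaves a counting rule unstated for a contingency that may never arise, and section 6.3 points to the sensible answer: REDCap exercise entries take the place of app entries over the same study period days. An analyst facing a switch would count them that way and report how many patients were affected. It goes too far to call the assurance in 6.3 wrong; it is loosely worded.

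The effect is zero without a switch, and the documents give neither the likelihood of one nor the number of patients it would reach. With a switch, data already collected are unchanged and the exact intervals overlap widely. Only the point-estimate verdict close to 70% can move, as in 12/17 against 11/17. This rests on reading REDCap as a replacement entry route and, for the day limits, on counting every calendar day of the intervention.
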